### **Specific Aims**

The Compensation examination that determines if a Veteran is entitled to any disability payments related to military service is a crucial gateway to accessing VA care for returning OEF/OIF/OND Veterans. However, researchers and oversight agencies have noted that examiners typically do not have guidelines for evaluating comorbid conditions like substance abuse and for referring patients to treatment.

In the Evaluative Component of this study, OEF/OIF/OND Veterans presenting for Compensation evaluations for PTSD will be approached to undergo a paid battery of confidential substance use, PTSD, service use and attitude assessments prior to their scheduled Compensation examinations. The batteries will be collected again twice, four and twelve weeks after the Compensation examinations. Long-term follow-up data will be extracted from VA databases including diagnoses, the results of the Veterans' Compensation evaluations, award determination, use of VA services and attendance at mental health and/or substance abuse treatment.

In the Clinical Trial Component of this study, one hundred sixty Veterans identified during the baseline evaluation as having a substance use disorder will be randomly assigned to a session of Screening, Brief Intervention and Referral to Treatment (SBIRT) or to No-Additional-Treatment.

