#### Justification for Enrolling Veterans with Comorbid TBI:

Histories of TBI will be inextricably intertwined with histories of PTSD in OEF/OIF Veterans with PTSD. TBI, PTSD and substance abuse frequently co-occur and intoxication predisposes people to both TBI and PTSD (Parry-Jones, Vaughan et al. 2006). The prevalence of *possible* Traumatic Brain Injury among returning OEF/OIF Veterans was 19.5% in one 2008 survey and 15.2% in a widely cited study of army infantry soldiers returning from a one-year deployment in Iraq (Hoge, McGurk et al. 2008). The impact of TBI on outcomes is controversial, with one study in the New England Journal of Medicine noting that much of the impairment in one year follow-up of soldiers who had experienced TBI was accounted for by comorbid PTSD and depression (Hoge, McGurk et al. 2008). However, other analyses have suggested that even mild TBI is related to physical symptoms years after the initial injury (Vanderploeg,

Belanger et al. 2009). The cognitive effects of mild TBI are difficulties with processing speed, multitasking, and sustained effort; the behavioral effects of TBI are relatively non-specific.

When Veterans undergo baseline assessments with the data collector, a questionnaire used in VA to make a preliminary diagnosis of TBI will be administered (TBI Clinical Reminder). In addition, the Montreal Cognitive Assessment (MOCA) will be administered to determine the extent of cognitive impairment. A history of TBI, with or without cognitive impairment on the Montreal Cognitive Assessment, will be determined and will be included as a covariate in outcome analyses.

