#### 3. Schedule of Assessments:

Visit	Domain	Assessment
BL	Characterize Participants	Baseline Questionnaire (including TBI screen) MOCA
BL	Beliefs about Compensation	Disability Application Appraisal Inventory Disability Beliefs Scale
BL	Substance Use	SCID substance abuse module
BL, 4, 12	Substance Use	Substance Use Calendar
BL, 12	Alcohol Use	Ethyl Glucoronide
BL	PTSD	Life Events Checklist and Military Sexual Trauma Screen
4	Process	Veterans' understanding of the study assessments and their relationship or lack thereof to the C&P exam
BL, 4, 12	PTSD	CAPS
BL, 4, 12	Other Psych	Beck Depression Inventory II
BL, 4, 12	Service Use	Service Use Calendar
BL, 4, 12	Process	Stage of Change
BL, 4, 12	Other Psych	Response to Stressful Experiences Scale
At Rx	Process	Satisfaction with Therapy
End-of-Study	Chart Review and Database Extraction	Review of Service Use and Diagnoses from VA Databases; Reports from Compensation Examinations; Disability Determination by VBA; Distance between Veterans' addresses and VA site

Justification for Schedule of Assessments: The initial 4-week assessment follow-up date was chosen because results of Motivational Interviewing interventions have been detectable this quickly in other studies (Burke, Arkowitz et al. 2003); the later, week 12 assessment will allow for detection of later-emerging effects of other VA treatments preferentially attended by Veterans who received the SBIRT intervention.

The end-of-study service use assessments will be conducted in the middle of year 4. Virtually all of the last cohort of study participants will have service use data for the three months after claims adjudication available at that time; the highly-publicized delays in the awarding of benefits generally are caused by delays prior to the Compensation evaluation.

Time to Complete Assessments: The baseline assessment will take approximately two and a quarter hours to complete. Approximately 45-60 minutes are allotted for the CAPS and Life Events Checklist; ten minutes for each of the baseline questionnaires, SCID substance abuse module, and service use calendar; and twenty minutes for each of the other baseline assessments.

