#### 4. Demographics and Other Characteristics

a. Baseline Characteristics Questionnaire: A questionnaire to characterize study participants has been culled from the questionnaire used in a prior multi-site study (Morrissey, Calloway et al. 2002) and in our current Benefits Counseling study. It is included as Appendix 2. It covers the following domains: demographics, military history, psychiatric history, employment, and legal status. It will also include a six-item measure of social support and the 10 items from the Attitudes Toward Seeking Professional Psychological Help Scale-Short Form (Elhai et al., 2008). This widely-used scale consists of two factors, one reflecting openness to

seeking treatment for emotional problems and the other reflecting value of seeking treatment and need for it.

Social support is measured as the number of people from six categories that would loan clients \$100, provide them with a ride to an appointment or provide them with emotional support if they were suicidal (Lam and Rosenheck, 1999).

The Questionnaire also includes the VA four-question screen for a presumptive diagnosis of TBI. A presumptive diagnosis of TBI is made when the Veteran responds positively in each of four domains:

- i. History of Potential Head Injury (e.g. blast, vehicular accident, wound above shoulders)
- ii. Symptoms Immediately After Injury (e.g. being dazed, not remembering event)
- iii. Problems Afterwards (e.g. memory problems or lapses, light sensitivity)
- iv. Problems in the Past 7 Days (e.g. memory problems, balance problems, headaches)

b. Montreal Cognitive Impairment Test (MOCA): The holders of the MOCA copyright allow its use within VA for non-commercial purposes. It is sensitive to impairment in domains prominently impacted by TBI such as visuospatial/executive functioning, attention, abstraction and in fact contains several items from the Core Brief Neuropsychiatric Battery (TBI Clinical Reminder) used at VHA to screen for TBI. A score of <26 indicates substantial cognitive impairment (Nasreddine, Phillips et al. 2005).

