### 4. Evaluation of Factors Associated with Treatment Effects

To determine what factors are associated with response to any kind of counseling, potential predictor variables will be entered into the primary outcome analyses as covariates. Potential predictor variables include gender, type of trauma, use of an illicit drug, baseline PTSD severity as measured by the CAPS, depression as measured by the BDI, a history of TBI, and cognitive impairment as evidenced by a score below 26 on the MOCA. As noted in the data analysis plan for the evaluative component, other potential moderator variables will include attitudes concerning Compensation exams (Veterans' reasons for seeking Compensation on the Disability Appraisal Inventory, and beliefs about whether Compensation is influenced by treatment attendance, continuing symptoms, and substance use on the Disability Beliefs Scale).

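### Section K.4 enters cognition only as MOCA below 26 versus not; the MOCA total score, already collected at baseline, would be the more efficient predictor if the relation with outcome is roughly linear

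*Combined protocol and SAP*

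**What the plan says.** Section K.4 (Evaluation of Factors Associated with Treatment Effects) states that "potential predictor variables will be entered into the primary outcome analyses as covariates". Its list includes "baseline PTSD severity as measured by the CAPS, depression as measured by the BDI", both without a cut-point, and then "cognitive impairment as evidenced by a score below 26 on the MOCA".

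The graded score will exist. The Schedule of Assessments places the MOCA at the baseline visit. The section justifying enrolment of Veterans with TBI says that the MOCA "will be administered to determine the extent of cognitive impairment". Section G.4.b gives the threshold, citing a published source: "A score of <26 indicates substantial cognitive impairment". That sentence says how to read one person's score. It does not say how the score should enter a model.

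The only other analysis that names cognition as a possible predictor is J.8, in the Evaluative Component. It mentions cognitive function without a cut, but only if bivariate analyses suggest it.

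**The concern.** A cut at 26 treats a Veteran scoring 25 as different from one scoring 26, and treats all Veterans on the same side of the cut as alike. If outcome changes gradually with cognition, the variation within each group is thrown away and the association is harder to detect.

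The plan elsewhere separates a diagnostic threshold from a regression predictor. The CAPS has its own diagnostic rule, which includes a total severity of at least 45 (J.2.c), yet K.4 uses CAPS severity uncut and J.5 uses the CAPS total score as a covariate. The Disability Beliefs subscales are to be analysed as continuous scores (G.5.b). Among the severity scales named in K.4, the MOCA is the exception, and no reason is given.

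What is at stake is the sensitivity of one secondary predictor analysis in a randomized sample of 160.

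**Working it through.** **Inputs from the documents.** Randomized sample: "one hundred sixty Veterans identified during the baseline evaluation as having a substance use disorder will be randomly assigned". The Power Analysis for the Clinical Trial Component gives 128 evaluable, standardized effect 0.50, power 0.80, alpha .05 and an allowance for 20% loss. Sidedness is not stated; two-sided is assumed here.

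**Inputs that the documents do not give.** Share below 26 (p), distribution of the MOCA, size of its association with outcome, and any power target for K.4. These are assumptions below.

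**Step 1: the plan's own figure.** As a two-group approximation to the linear-trend calculation, n per arm = 2 × (1.960 + 0.842)² / 0.50² = 62.8, so 63 per arm and 126 in total. With the noncentral t distribution, 64 per arm (128 in total) gives power 0.801. Then 128 / 0.80 = 160. The stated sample size reproduces, but it concerns the treatment comparison and gives no power for K.4.

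**Step 2: information lost by the split.** For a normal score with a linear relation to outcome, cutting at prevalence p multiplies the correlation by a = φ(z_p) / √(p(1−p)), where φ is the normal density at the cut. The information kept is a².
- p = .50: a = 0.399 / 0.500 = 0.798; a² = 0.64; about 36% lost.
- p = .10: a = 0.1755 / 0.300 = 0.585; a² = 0.34; about 66% lost.

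**Step 3: illustration as power.** Fisher's z at N = 160: the correlation that gives 80% power on the full score is r = tanh((1.960 + 0.842) / √157) = 0.220. This r is solved for, not taken from the documents. Power after the split is Φ(atanh(a·r) × √157 − 1.960).

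| Share below 26 | a | a² | Power, full score | Power, split | Loss (points) |
|---|---|---|---|---|---|
| 50% | 0.798 | 0.64 | .80 | .60 | 20 |
| 30% | 0.759 | 0.58 | .80 | .56 | 24 |
| 20% | 0.700 | 0.49 | .80 | .49 | 31 |
| 10% | 0.585 | 0.34 | .80 | .37 | 43 |

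At N = 128 (r = 0.245) the split powers agree to within a point.

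**Step 4: how far this depends on the assumptions.**
- Weak association (r = .10): power on the full score is only .24 at N = 160 and .20 at N = 128. The loss is about 6 to 13 points over p = 50% to 10%.
- Full score with 95% power: the loss is about 14 to 41 points over the same range.
- Left-skewed, discrete scores with about 9% to 51% below 26: the loss is about 19 to 31 points.
- True relation a step exactly at 26: the binary form is the more powerful one and nothing is lost.

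**The case against.** The cut is a recognised clinical threshold fixed in advance, so it is not data-driven. The section on TBI also treats impairment as a category when it says that TBI history, with or without impairment on the MOCA, will be a covariate. Cognition appears in no hypothesis, and K.4 claims no power. The power figures come from a bivariate correlation test, whereas K.4 adds several predictors, possibly correlated with each other, to random effects regressions on repeated outcomes. All of this stands. It limits the size and importance of the point, but it gives no reason to prefer the binary form. J.8 is conditional and belongs to the Evaluative Component, so it does not supply a continuous analysis in section K.

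A reader might infer more than the documents support, in three ways.
- That K.4 is the trial's reason for enrolling Veterans with TBI, so that a null result would be read as endorsing broad enrolment. The enrolment section rests on the overlap of TBI, PTSD and substance abuse. It does not tie enrolment to K.4.
- That a null result for cognition is likely. In the illustration, power after the split is still 56% to 60% when 30% to 50% score below 26.
- That the plan loses 20 to 43 points of power as a fact. That range needs a linear relation, a normal score, 80% power on the full score, and 10% to 50% of Veterans below 26. The documents supply none of these.

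**Conclusion.** The point holds as a modest efficiency improvement. K.4 reduces a graded baseline measure to two categories without a stated reason, while comparable scales in the same list are left whole. Under a roughly linear relation and a roughly normal score, between about 36% (half below 26) and 66% (10% below 26) of the information on cognition is discarded. The power figures of 60% and 37%, against 80%, illustrate that loss in a simple correlation test and should be quoted only with their conditions. They were not computed for the random effects models in the plan. The primary SBIRT versus No-Additional-Treatment comparison, its sample size and the separate TBI-history predictor are untouched.

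**What to change.** In K.4, replace the impairment category by the MOCA total score, entered as a continuous predictor, and use the same form in any treatment-by-cognition term. Keep the below-26 category for the baseline table and as one pre-specified sensitivity analysis, which covers a threshold effect. Specify both forms now, so that the choice between them does not depend on the data.

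The cost is about one line of text, with no new data, visit or change to the primary analysis. The downside is that the main result is reported per MOCA point rather than as impaired versus not impaired; the sensitivity analysis still gives the clinical contrast.

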### 5. Evaluation of Process Measures

Group X Time random effects regression analyses will be conducted to determine differential effects of time on Stage-of-Change, which is collected at multiple time points. The Likert-scaled therapy process ratings and other measures reflecting single values (e.g. duration of therapy sessions) will be compared between groups using ANOVAs.

## Human Subjects

### A. Consent Procedures

1. Recruitment: A waiver of written informed consent and HIPPA authorization will be obtained to review the names and contact information of OEF/OIF/OND Veterans requesting a new PTSD examination [we will secure lists of new applicants either directly from VBA or from the Compensation and Pension office, as provided by VBA], and to review electronic medical charts for basic eligibility criteria, including age, theater of military service, and percent service connection for PTSD. The waiver will allow for the collection of basic demographic information

concerning Veterans screened for study participation to determine if Veterans who consent to study participation differ systematically from those who do not.

Letters explaining the study will be sent Express mail to Veterans applying for a PTSD examination. The letter explains that a member of the research team will telephone the Veteran to invite the Veteran to participate in the study, but that the Veteran can opt out of receiving this telephone call by calling a confidential telephone number. If the Veteran does not opt out within 6 days of the mailing, the Veteran will be called, and the study will be explained to him/her. Up to three attempts will be made to contact the Veteran for recruitment before we will stop attempting. Interested Veterans will be invited to complete a consent form and begin the Evaluative Phase and baseline evaluations of the study.

2. Consent: Voluntary informed consent will be obtained from all Veterans prior to participation. Consent will be obtained by one of the investigators or his/her designee after the research procedures and risks associated with participation have been explained to the candidate. A signed copy of the consent form will be provided to all potential Veterans.

Participants will be asked several questions to be certain they understand the risks associated with study participation. Only participants who correctly answer all the questions (with a second chance to answer questions if incorrectly answered the first time) will be enrolled. The questions will be the following:

a. What topics will you be asked about?

Answer should mention PTSD and substance use.

b. Will the things you tell the research assistant be told to the VA people who decide on your service-connection?

No.

c. Can you drop out of this study whenever you want?

Yes.

## B. Risks

Risks associated with participation in the study include risks associated with:

1. *Completing questionnaires*: Administration of study instruments may be boring, frustrating, or upsetting.

2. *Becoming upset while discussing traumatic events*: There is a risk that individual Veterans will become upset by discussing their traumatic events during assessments or therapy. Veterans report drinking to manage their PTSD symptoms, so there is a risk that upset from discussing traumatic events could lead to increased substance use (Bremner, Southwick et al. 1996). In practice, study-related adverse events in clinical trials of PTSD treatments among Veterans have been very rare (Schnurr, Friedman et al. 2007; Monson, Gradus et al. 2008). Research assistants will emphasize that answering questions is voluntary and will allow Veterans to answer questions at their own pace and without duress

3. *Information from the counseling being told to participants' clinicians at the VA or to someone who reviews their disability application*. The counseling is unlikely to impact the Veteran's disability. The therapist will not volunteer any non-emergent information in the Veterans' chart or to other clinicians, as this is contrary to the voluntary, Motivational Interviewing stance that is integral to SBIRT. The therapist will write a note in the Veteran's VA chart after therapy indicating that the participant was in a research study and met with the therapist.

Nevertheless, the SBIRT therapist is going to convey information to other VA clinicians if the Veteran indicates information during the therapy that requires emergent intervention by another VA clinician. If the Veteran indicates information suggesting imminent danger to the Veteran or to others, the SBIRT therapist will share this information with other VA clinicians so

they can take appropriate action. Therefore, veterans will be told the risk that information that they tell the study therapist may be told to their VA clinicians and would then become available to someone who reviews their disability application.

Even if the emergency disclosure includes disclosing the presence of a substance use disorder, this is unlikely to prevent receipt of service-connected disability. Veterans who have substance use disorders may still be judged to have service-connected PTSD. In light of the frequent comorbidity between PTSD and substance abuse described earlier, it would be unreasonable for VBA to insist that a Veteran be abstinent to be diagnosed with PTSD. In an oft-cited "Allen" court case decided by the Federal Appeals Court (Allen v. Principi Judicial Decision [99-7199](#)), the court ruled that substance use, when it was a consequence of service-connected PTSD, could in fact itself be an additional, reimbursable consequence of military service.

4. *The three people whose names the Veteran provides may find out that the Veteran is in a research study.* If we are unable to contact the Veteran directly for assessment visits, we will contact the three people whose names the Veteran gave us and ask them if they know how to contact the Veteran. If a member of our staff contacts any of these people, the staff member will say that he (or she) works on a research study at VA. Therefore, we will inform Veterans that if they do not want anyone they know to be called by someone identified as being from a VA research project in order to contact them, then they should not participate in this study.

### C. Protection of Participants

1. Confidentiality: All research information is considered confidential. Limits to confidentiality include only disclosure of acute suicidality, homicidality, or abuse of a minor, as is standard in clinical practice. Suicidal ideation will be revealed to clinical staff if a Veteran selects either of the following on the Beck Depression Inventory: "I would like to kill myself" or "I would kill myself if I had the chance." *If a Veteran reports any of the following, the person it is reported to (therapist or data collector) will contact the site investigators and if the investigator is not available, the clinician handling intakes for the respective PTSD firms.*

Both study sites have emergency room facilities and a suicide prevention coordination team. The participant's condition will be assessed by a VA provider. The RA will attempt to facilitate this by contacting the clinical intake coordinator. The PI will also be contacted. The RA will accompany the Veteran to an immediate evaluation by a clinician or assessment in the Emergency Department. Part of the RA training will be learning where these facilities are located.

Research data will be identified by code number and will not include names, although enrollment records must also be kept and these records will include names. Our study forms have been designed to avoid collecting identifiable information; no Protected Health Information (PHI) will be collected on study forms. We generally collect only protocol session dates. These dates are changed to 'number of sessions completed' when data sets are anonymized and released to other investigators. Research data, containing no PHI, are brought to the West Haven VA for scanning and outputting to databases using Teleforms Software. All computers used by research staff are password protected.

Study data will be stored and analyzed in the VA Informatics and Computing Infrastructure (VINCI). VINCI is a Department of Veterans Affairs (VA) Health Services Research & Development (HSR&D) resource center that provides a secure, central analytic platform for performing research and supporting clinical operations activities. It is a partnership between the VA Office of Information Technology (OI&T) and the Veterans Health Administration Office of Research and Development (VHA ORD). VINCI includes a cluster of servers for securely hosting suites of databases integrated from select national VA data sources. VINCI servers for data, applications and virtual sessions are physically located at the VA Austin Information Technology Center (AITC), located in Austin, Texas. This secure enclave

with 105 high-performance servers and 1.5 petabytes of high-speed data storage has multiple layers of security and disaster recovery to prevent data loss. To ensure the protection of Veteran data, VINCI maintains compliance with the guidelines set forth by Veterans Health Administration (VHA) Handbook 1200.12, Use of Data and Data Repositories in VHA Research, and all other applicable VA and VHA policies and regulations. In addition, VINCI has undergone all security certification activities in support of obtaining an Authorization to Operate (ATO). Access to VINCI resources are approved in accordance with the requirements of National Data Systems (NDS), VHA Handbook 1200.12, Use of Data and Data Repositories in VHA Research, and all other applicable VA and VHA policies and regulations. All data transferred from VINCI is subject to audit for compliance. VA-credentialed research staffs are granted access to study-specific data along with tools for analysis and reporting in the secure, virtual working environment through a certified VHA network computer within the VA. If not working within a VA or VHA hosted office environment containing VA network access, researchers may apply for and then access VINCI through an approved Virtual Private Network (VPN) and Remote Desktop application. The remote computing environment enables data analysis to be performed directly on VINCI servers, offering a number of advantages: uniform security standards for access; a common point of entry for all investigators who use the data; tools for analysis and reporting; tighter and more consistent control of data quality; and the ability to standardize and update terminology and format as technology and methodology improve.

Personal identifiers will be retained to obtain VA service use data from Austin in year 4 of the study. The personal identifiers will be used to identify service use by study participants from the Outpatient Encounter File and Patient Treatment Files. After the data is extracted, the identifiers will be removed from the Austin files to create files with de-identified data for subsequent analyses.

All possible precautions will be taken to prevent a breach of confidentiality. Study IDs will be assigned at the time of recruitment and replace names and record numbers. Clinical enrollment records are kept separate from research data, and are not available without a Veteran's written consent. Participants' names will appear only on the consent form, HIPAA authorization form, and "key" form kept by the site PI. At the conclusion of the study, all locator data will be destroyed. The crosswalk file will be stored separately from all other study data on VA secure network computers. Data Security will be insured via the servers, which all reside completely behind the VA firewall. All systems utilize Secure Socket Layer (SSL) technology for internet protocol data transfer, which encrypts all network transmissions and transmits only within the VA network backbone. There is no public internet access. Another layer of protection for sensitive information is ascribed to the system by use of granular access privileges. Only site-specific authorized staff will have data access. Study managers have the capability of granting access and read-write privileges to users. All systems undergo daily backup and 24-hour security.

Outcome data will be collected on paper forms that will be scanned into PDFs that are in turn outputted to study databases by Teleforms software using object-character recognition. Forms will be labeled by study numeric ID; names and other Personal Health Information identifiers such as social security numbers will not be used on study material. The forms will be scanned at each site into electronic PDF files and electronically uploaded to the study data repository. Naming conventions will be instituted for all files using study ID codes. The commitment of data from the forms to SPSS databases will be carried out at West Haven using Teleforms software. Source documents (e.g. Compensation and Pension examinations) are stored on VA clinical servers behind a secure firewall, and will not be stored with research data.

All paper forms will be stored and secured in a locked file cabinet under the jurisdiction of the site P.I. The site PI will be responsible for oversight of local data collection.

The research records will be used to prepare reports that do not include patient identification.

All research staff and therapists receive annual Good Clinical Practice, Human Subjects Protection, HIPAA, and VHA privacy training through the VA. Our data collection and management procedures are fully compliant with HIPAA.

To reduce the possibility of identifying participants and associating outcomes with their identities, nail samples will be coded with non-informative ID numbers.

A Certificate of Confidentiality has been obtained to minimize the risk of forced disclosure in a legal or other proceeding. The Certificate, and the study consent form, will indicate the exceptions to confidentiality in which information may be disclosed without a patient's consent.

2. Confidentiality of Videotapes: To assure the confidentiality and protection of participants with respect to videotaping, the following steps will be taken:

- Participants will provide informed consent for videotaping. Participants will be allowed to participate in the study and refuse the videotaping. Participants who do consent to videotaping will be informed that they have the right to stop taping at any time during the session.

- Therapists will videotape their own sessions to eliminate the need for a technician in the room.

- As therapist behavior is of primary interest, the camera will be directed at the therapist. The participant's voice will be recorded on the videotape.

- Video recordings will be treated as confidential research records. The videotape, labeled with a unique study ID code will be uploaded to a secure network VA server, separate from other study data. The file name will use study ID codes.

- Access to videotapes will be limited to members of the investigative team including trained research raters who will rate the tapes according to the therapist adherence and competence rating systems and only the research staff will have access to the recordings. A separate file will link the videotape file code to the participant's unique identification code, the therapist name, and the date of the session.

3. Testing. Subjects will be given breaks during the test battery to minimize frustration, fatigue, and psychological discomfort. The research assistant administering these tests will be trained in the use of these standardized instruments and knowledgeable about cultural differences within the study population.

4. Training of Study Therapists: The risk of angering or alienating Veterans is very small because of the non-confrontational nature of SBIRT. The risk will be further minimized by hiring staff who have experience with the study population. Study therapists will be trained to adopt a collaborative approach. Study therapists will also be taught where the emergency facilities are including the location of emergency rooms, VA and public police and crisis services. Study therapists will also receive training in de-escalating agitated Veterans.

5. Training of Study Data Collector: Data collectors will also be taught where the emergency facilities are including the location of emergency rooms, VA and public police and crisis services. Data collectors will also receive training in de-escalating agitated Veterans.

